3.1.3 MEG Assessments: Visits 1-3

On the next three visits (scheduled to occur within a range of 3-12 months of the clinical/behavioral testing) MEG, MRI, and MRS measures will be collected at each study visit in the Dept. of Radiology. MEG testing will last approximately 3 hours (pre- and post STX209 scanning, with 1 hour period between baseline and post-STX209 administration) and MRI will take approximately an additional 1 hour (after the post-MEG exam) For MRI, no sedation or contrast will be used.

Specifically, we will accept behavioral testing within a 6-12 month timeframe and will accept Blood Draw results and Physical Examination review within 3 months of the first imaging visit. For cases where there has been a 3 month or more lag between screening visit and imaging visit, the Blood Draw and Physical Exam will be repeated to ensure safety and adequate monitoring (as noted above, in cases where subject is unable to do a blood draw on the day of the screening visit due to anxiety/fear/discomfort if no medical risk factors are identified during medical history review, we will either accept BUN and Creatinine results from an outside source within 3 months of first imaging visit or attempt to do the blood draw on the day of the imaging visit.).

Upon arrival, MEG data will be collected to obtain baseline measures. At the conclusion of the baseline MEG scan, participants will be randomly administered a single dose of placebo and in order of increasing order a single-dose of STX209 (15mg and 30mg). Based on advice from Seaside Therapeutics, given the time course of plasma STX209 levels, the MEG examination will be repeated 60 minutes after drug administration. Following the MEG exam, subjects will obtain a 3T MRI to obtain an anatomic 3D image (MP-RAGE) and bilateral STG GABA and glutamate measures (MEGAPRESS MRS). Subjects will return for their imaging study visits no less than four days or more than 14 days to repeat the MEG and MRI and MRS exams, each time with a different drug/placebo dose.

3.2 Blinding

Across three visits, participants will be randomly assigned a single dose of placebo, and in order from smallest to largest a single-dose of STX209 (15mg, and 30mg). Participants will be blind to dosage order. Clinical Research Associates, LLC (CRA) will provide the needed STX209 tablets and identical placebo tablets. For each subject, the pharmacist at CHOP will create three 2-pill combinations. Order of the STX209/placebo conditions will differ for each subject. Upon entry into the study, the study pharmacist will assign each subject to one of the below dosage orders, and at each visit providing the research coordinator with the needed pills for that particular visit.

Option 1	Option 2	Option 3
Placebo	15mg	15mg
15mg	Placebo	30mg
30mg	30mg	Placebo

Subjects will receive study drug regimen in increasing dosage from smallest to largest and a randomly administered single-dose of placebo.

3.3 Study Duration, Enrollment and Number of Sites

3.3.1 Duration of Study Participation

40 participants will take part in a 4-week placebo controlled, randomized, acute dose response trial. Participation will be extended up to six or eight weeks if subjects are unable to come in 4 consecutive weeks in a row. Subjects will first come in for their screening visit followed by 3 MEG/MRI/MRS assessment visits (total of 4 visits).

3.3.2 Total Number of Study Sites/Total Number of Subjects Projected

The study will be conducted at one investigative site in the United States – at the Children’s Hospital of Philadelphia. The clinical and neuropsychological testing will occur at the Roberts Pediatric Center at the Children’s Hospital of Philadelphia ([name]) or at Main Hospital or at Clinical and Translational Research Center at [name] and the medical evaluation on screening

visit and Visit 3 will occur either at the Clinical and Translational Research Center at [name], or at the main hospital at [name]. [name], M.D., a Developmental-Behavioral Pediatrician at the Children's Hospital of Philadelphia will be the primary physician on this project.

We will enroll 40 subjects in order to get 38 evaluable subjects.

3.3.3 Inclusion Criteria

- 1) Males aged 14 to 17.75 years.
- 2) Confirmation of diagnosis of ASD within the past 12 month, according to the DSM-IV criteria, including Autism, Pervasive Developmental Disorder – Not Otherwise Specified (PDD-NOS), and Asperger's Syndrome but excluding Childhood Disintegrative Disorder and Rett Syndrome.
- 3) Current pharmacological treatment regimen has been stable for at least 4 weeks prior to Screening.
- 4) If the subject is already receiving stable non-pharmacologic educational, behavioral, and/or dietary interventions, participation in these programs must have been continuous during the 2 months prior to Screening and subjects or their parent/caregiver may not electively initiate new or modify ongoing interventions for the duration of the study. Typical school vacations are not considered modifications of stable programming.
- 5) Prior to the conduct of any study-specific procedures, the subject must provide verbal assent to participate in the study (if developmentally appropriate), and the parent/caregiver must provide written informed consent. If the caregiver attending the clinic visits is not the parent, written consent must be obtained from the parent for the caregiver's participation in the study.

3.3.4 Exclusion Criteria

- 1) No known neurological impairment (e.g., head trauma with loss of consciousness for more than 10 minutes, stroke, seizure disorder).
- 2) Claustrophobia
- 3) Metallic implanted prosthetic or stimulation device (including pacemaker)
- 4) Excessive metallic dental work (including braces, non-removable retainers)
- 5) Subjects who are currently receiving treatment with racemic baclofen, vigabatrin, tiagabine, or riluzole.
- 6) Subjects who have taken another investigational drug within the last 30 days.
- 7) Subjects who are not able to take oral medications.
- 8) Subjects who have a history of hypersensitivity to racemic baclofen.

- 9) Any concomitant medication deemed necessary for the welfare of the subject during the study may be given at the discretion of the Investigator. No more than 2 psychoactive medications (including antiepileptics) may be used with the exception of medications being combined to treat ADHD symptoms and sleep problems. Psychoactive medications must be FDA-approved for use for the disease or symptom being treated; off-label use is not permitted. If the subject is taking fewer than 2 psychoactive medications, and during the study it is deemed the subject needs an additional psychoactive medication, the Medical Monitor must be consulted before the subject can continue in the study. Antipsychotic medications are not permitted.

Medications with anxiolytic properties (serotonin re-uptake inhibitors, tricyclic antidepressants, venlafaxine, buspirone, and propranolol) are not permitted. Melatonin, diphenhydramine, and other medications administered regularly for insomnia are permitted. The use of vigabatrin, tiagabine, riluzole, or racemic baclofen is prohibited

- 10) Parents/guardians or subjects who, in the opinion of the Investigator, may be non-compliant with study schedules or procedures.

4 STUDY PROCEDURES

4.1 Screening: Phone

Participants who respond to our recruitment procedures will be called by a Research Assistant. These trained staff members will describe the intent of the study, what is involved for the child and parent, and discuss basic elements of the consent (**Study Description Phone Script and Informed Consent for Phone Screening**). The parent/guardian will be invited to complete a brief, preliminary screening interview in order to determine eligibility for the study and will be consented via the telephone for an eligibility screening. If parents/guardians choose not to continue or decline to consent to screening, they will be thanked for their time and asked if they would like to receive any information about research participation or clinical services. If so, general information about ongoing research and clinical services at CHOP will be provided (as described in the phone script).

Once the parent/legal guardian verbally consents to the screening call, trained staff will complete the “**Screen for Eligibility Criteria**”. This interview takes approximately 10 minutes to complete. *Upon completion, eligibility criteria will be reviewed immediately.* If the child is likely to meet eligibility criteria, the parent is invited to continue. A “**Pre-Visit Intake Questionnaire**” will be conducted over the phone with the parent of subjects who are both eligible for the study and want to participate. This short questionnaire needs to be completed prior to the subject coming in for his/her first study visit.

If the parent has endorsed any exclusionary criteria, they will politely be informed that they are not eligible for the current study and provided with the opportunity to seek referrals for other research projects or to be contacted by a clinician to receive appropriate clinical referrals.

4.2 Screening Visit

On the screening visit participants will be given Informed Consent and the following assessments and procedures will be administered to confirm eligibility and safety. Measures bearing on exclusion and inclusion criteria will be done first, and if determined eligible to participate, participants will complete the other measures.

- Neuropsychological evaluation, including both clinical and behavioral testing (*only if applicable*)
- Physical Examination (*include abdominal palpation to assess for liver enlargement, assessing for decreased tone and postural problems, increased drooling and poor orofacial tone, problems holding head up, and difficulty with coordination of motor actions*), *Height and Weight, and Medical/Surgical History Review*
- Vital Signs: *Temperature, Blood Pressure, Heart Rate, and Respiratory Rate*
- Blood Draw (*BUN and Creatinine*) (To minimize harm to the subject, in cases where subject is unable to do a blood draw on the day of the screening visit due to anxiety/fear/discomfort, if no medical risk factors are identified during medical history review, we will either accept BUN and Creatinine results from an outside source within 3 months of the first imaging visit or attempt to do the blood draw on the day of the imaging visit.)

4.3 MEG and MRI/MRS Assessment Phase: Visit 1-3

On the next three visits (scheduled to occur within 3 months of the physical examination and within 12 months of clinical/behavioral testing) MEG, MRI and MRS measures will be collected at each study visit. Upon arrival, vital signs will be collected. Then pre-drug MEG data will be collected to obtain baseline measures. At the conclusion of the baseline MEG scan, participants will be randomly administered a single-dose of Placebo and single-dose of STX209 in order of smallest to largest dose (15mg, 30mg) (see Section 3.2). Based on advice from Clinical Research Associates, LLC (CRA), given the time course of plasma STX209 levels, the MEG examination will be repeated 60 minutes after drug administration. Following the MEG exam, subjects will obtain a 3T MRI to obtain an anatomic 3D image (MP-RAGE) and bilateral STG GABA and glutamate measures (MEGAPRESS MRS). At the end of the scanning visit AE will be assessed via the SMURF form. Subjects will return for their imaging visit no less than four days or more than 14 days to repeat the MEG, MRI and MRS exams, each time with a different drug/placebo dose.

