5.1.3 Physical Examination

[name] will perform the physical examination (screening visit and visit 3) at the Clinical and Translational Research Center located at [name] or at Main Hospital. However, for the imaging visits (visit 1-visit 3) the SMURF will be performed at the Department of Radiology to assess for adverse events. This can be performed by either [name] or a trained research staff under the guidance and supervision of [name].

- 1) *Physical Examination: A Physical examination will be performed at Screening and at Visit 4. Physical examination findings will be classified using the standard categories listed on the CRF. A brief physical examination will be performed at screening visit and visits 1 through 3 and will include abdominal palpation to assess for liver enlargement, assessing for decreased tone and postural problems, increased drooling and poor orofacial tone, problems holding head up, and difficulty with coordination of motor actions. Any physical examination finding that is judged by the Investigator as a clinically significant change (worsening) from screening visit will be considered an AE, assessed and recorded on the CRF.*
- 2) *Height and Weight: Height and weight measurements must be performed without shoes on, and with only a single layer of light clothing. Height and weight measurements should be performed using consistent units (US).*
- 3) *Medical/Surgical History Review: The study doctor will review Medical/Surgical History*
- 4) *Safety Monitoring Uniform Report Form (SMURF): The SMURF contains a general inquiry, several questions about daily activities (e.g., sleep, appetite, energy level, bowel and bladder function). The general inquiry includes an open ended question about any problems or complaints, as well as questions regarding the need for other medications and doctor or health care encounters since the last study visit. The next section includes 20 to 25 specific queries. These items are rated as not present, mild, moderate or severe. The ratings mild, moderate, or severe are defined as follows: mild=present, but no intervention required; moderate=present, may be bothersome or may require intervention; severe=present, bothersome and requires intervention. The last section includes specific questions about daily activities. All new adverse events (mild, moderate, or severe) will be documented. The status of previously reported adverse events will be monitored as well.*

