Screen for Eligibility Criteria	10 min
Pre-Intake Questionnaire (Demographics)	20 min
Subtotal:	75 min
Screening Visit:	
Medical, Diagnostic, and Neuropsychological Assessments	
Procedures administered to Parent/Legal Guardian (at the same time as child testing)	
Intervention History Form	15 min
Medical History Form	30 min
Child Behavior Checklist (CBCL) (if applicable)	20 min
Social Communication Questionnaire (SCQ) (if applicable)	5 min
Social Responsive Scale-II (SRS-II) (if applicable)	10 min
Vineland Adaptive Behavior Scale (if applicable)	20 min
Autism Diagnostic Observational Scale (ADOS-2) (if applicable)	60 min
Subtotal:	2 hours and 40 min
Procedures individually administered to children:	
Physical Examination	15 min
Blood Draw	10 min
Vital Signs	10 min
Clinical Evaluation of Language Fundamentals (CELF –IV)	
(if applicable)	60 min
Wechsler Abbreviated Scale of Intelligence (WASI-II) (if applicable)	60 min
Baseline SMURF	20 min
MRI Mock Scan (optional)	30 min
Subtotal:	3 hours and 25 min

* Diagnostic and neuropsychological testing will not occur if testing scores are available (less than 12 months prior to screening visit) for re-recruited participants (data from tests will only be used if subjects who previously participated in one of our research studies, agreed to share their data on future studies). Only the medical assessments (e.g., vital signs, physical exam, medical history, intervention history form, and blood draw) will be completed for re-recruited participants at screening visit. Therefore, the screening visit will last approximately 80 minutes for re-recruited participants.

MEG Assessment 1: Visit 1

Procedures individually administered to participants at Visit 1	
Autism Diagnostic Interview – Revised (ADI-R) (if applicable)	180min
Vital Signs	10 min

Pre Drug MEG Scan	45 min
MRI Scan	30 min
Administration of STX209/Placebo	< 10 min
MRI Scan continued	30 min
Break	30-60 min
Post Drug MEG Scan	45 min
Adverse Event Assessment (SMURF)	20 min
Subtotal:	4 hours and 50 min

MEG Assessment 2: Visit2

Procedures individually administered to participants at Visit 2	
Vital Signs	10 min
Pre Drug MEG Scan	45 min
MRI Scan	30 min
Administration of STX209/Placebo	< 10 min
MRI Scan continued	30 min
Break	30-60 min
Post Drug MEG Scan	45 min
Adverse Event Assessment (SMURF)	20 min
Subtotal:	4 hours and 10 min

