MEG Assessment 3 + Close Out: Visit3

Procedures individually administered to participants at Visit 3	
Vital Signs	10 min
Pre Drug MEG Scan	45 min
MRI Scan	30 min
Administration of STX209/Placebo	< 10 min
MRI Scan continued	30 min
Break	30-60 min
Post Drug MEG Scan	45 min
Physical Examination	15 min
Adverse Event Assessment (SMURF)	20 min
Subtotal:	4 hours and 40 min

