7 SAFETY MANAGEMENT

Clinical adverse events (AEs) will be monitored throughout the study.

Subject safety will be monitored by adverse events, blood draw, vital signs, and physical examination findings and concomitant medication usage.

[name] or the developmental behavioral pediatrician on call, will be on call during all MEG exams. Specifically, [name] will review pre-MEG vital signs (either in person or over the phone) prior to medication administration. [name] will administer the SMURF and evaluate the vital sign pre-and post-MEG in person for the initial and final study visits. For the visits in between SMURF and vital signs pre- and post-MEG will be done by an approved study staff and [name] will be on call to evaluate the results.

All tests will be promptly reviewed by one of the psychologists on the study team. Any clinical significant findings will be verbally reported to the parent-- either in person during the study visit or later via telephone, depending on when the concern is identified. Parents will be provided with mental health services referrals or will be advised to take their child to a hospital emergency room in the event of an acute care concern.

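### The SMURF is placed once, at the end of each imaging visit, in 4.3 and 5.2.1 but before and after MEG in Section 7; under the single form, later events after 15 mg are first asked about after 30 mg in two of three orders

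*Combined protocol and SAP*

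**What the plan says.** Section 4.3 sets the order of an imaging visit. It opens "Upon arrival, vital signs will be collected. Then pre-drug MEG data will be collected to obtain baseline measures"; the dose, the repeat MEG and the MRI/MRS follow, and then "At the end of the scanning visit AE will be assessed via the SMURF form". No symptom inquiry is listed before the dose.

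Section 5.2.1 itemises Visits 1 to 3. Each list has a single 20-minute entry, "Adverse Event Assessment (SMURF)", placed after the post-drug MEG. The stated total for Visit 2 is "4 hours and 10 min".

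Section 7 reads differently. For the first and last visits the study physician "will administer the SMURF and evaluate the vital sign pre-and post-MEG in person for the initial and final study visits". For the others, "For the visits in between SMURF and vital signs pre- and post-MEG will be done by an approved study staff". The check it explicitly ties to dosing is that the physician "will review pre-MEG vital signs (either in person or over the phone) prior to medication administration".

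Table 1 marks the SMURF and the adverse event assessment at Visits 1, 2 and 3, with no time within the visit. Section 5.1.3 describes the SMURF's general inquiry as including "questions regarding the need for other medications and doctor or health care encounters since the last study visit". Section 5.5 makes safety and tolerability a secondary endpoint. Section 5.6.4 summarises events by type, body system, severity and relationship to drug, and does not mention dose condition.

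**The concern.** Staff following 4.3 and staff following Section 7 would collect different safety data. If the single end-of-visit form is what happens, two gaps open.

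First, a symptom reported on that form has no same-day pre-dose comparator. The background rate of events can be high: in Study 22001, 71.4% of subjects reported adverse events during treatment with STX209 and the same percentage during placebo. The screening SMURF is a weak substitute. Table 1 puts it nominally a week before Visit 1, and 4.3 allows imaging up to three months after the physical examination.

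Second, each subject receives 15 mg before 30 mg, an order that 5.7 attributes to an FDA requirement. Under the single form, some subjects receive 30 mg before anyone has asked, in a structured way, what began after they left the 15 mg visit. No between-visit call is scheduled.

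**Working it through.** **1. Does the plan's own timetable imply one form or two?** Adding the Visit 2 items in 5.2.1, with dosing at 10 min and the break at 60 min:

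10 + 45 + 30 + 10 + 30 + 60 + 45 + 20 = 250 min = 4 h 10 min.

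This reproduces the stated subtotal with one SMURF. The evidence is weak. A 30-minute break with two SMURFs and two sets of vital signs also gives 250 min (220 + 20 + 10). The other subtotals do not match their items: Visit 1 is stated as 4 h 50 min, against 7 h 10 min with the ADI-R or 4 h 10 min without; Visit 3 is stated as 4 h 40 min, against 4 h 25 min. The itemised entries, one SMURF per visit, are the better evidence.

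**2. When does the end-of-visit form fall after dosing?**

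- 5.2.1 list, Visits 1 and 2: rest of MRI 30 + break 30 to 60 + MEG 45 = 105 to 135 min (1.75 to 2.25 h).
- 5.2.1 list, Visit 3, with the 15-minute examination before the SMURF: 120 to 150 min (2.0 to 2.5 h).
- 4.3 order, with MRI after the second MEG: wait 60 + MEG 30 to 45 + MRI 60 = 150 to 165 min (2.5 to 2.75 h). The MEG duration is from 5.1.6 and 5.2.1, the MRI duration from 3.1.3.

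Overall, about 1.75 to 2.75 h.

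**3. When is an event that starts after the 15 mg visit's form next asked about?** Dose orders are from 3.2; visits are 4 to 14 days apart (4.3).

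| Order | Visit after 15 mg | Next end-of-visit SMURF is after 30 mg? | Condition at Visit 3 |
|---|---|---|---|
| placebo-15-30 | 30 mg | yes | 30 mg |
| 15-placebo-30 | placebo | no | 30 mg |
| 15-30-placebo | 30 mg | yes | placebo |

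Two of three orders are affected. If allocation is equal, which the plan does not state, that is 2/3 × 40 ≈ 27 subjects. With a pre-dose SMURF at every visit, the inquiry would precede 30 mg in all three orders. The last column shows that events starting after the final form follow 30 mg in two orders and placebo in one, with no later scheduled form in any.

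**4. How much of the exposure lies beyond the form?** Section 1.3.1.2 gives a half-life of 5.85 h and a Tmax of about 1 h. Under simple exponential decline, the share of exposure elapsed by time t is F(t) = 1 − 2^(−t/5.85):

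- F(1.75) = 0.187
- F(2.25) = 0.234
- F(2.75) = 0.278

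A one-compartment oral model with Tmax 1 h (absorption rate about 3.5 per hour) gives 0.159, 0.207 and 0.253. So about 72% to 84% of exposure falls after the form. This is a proxy only. The figures come from healthy adults given 5 mg, and the documents do not link event timing to share of exposure.

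**The case against.** The strongest reply is that Section 7 already deals with this. Section 4.3 does not say that the end-of-visit SMURF is the only one. It also omits the post-MEG vital signs that Section 7 calls for, so it may be a summary. Read that way, a pre-MEG SMURF at Visit 2 covers the 15-30-placebo order. In placebo-15-30, however, the 30 mg visit is the last visit, where the pre- and post-MEG phrase may attach to vital signs alone. The reply shortens the problem but does not remove the conflict.

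Other safeguards also count. A physician is on call between visits, and families get contact instructions. Subjects who withdraw are contacted about adverse events (4.7.1). A brief physical examination is listed at Visits 1 to 3 in 5.1.3, with no time given. Section 7.2 requires date and time of onset, duration and causality. These limit the harm, but none is a scheduled symptom inquiry before the dose.

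Several stronger readings are tempting and not supported:

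- *Events after 15 mg go unasked until 30 mg.* Events in roughly the first two hours are asked about the same day, and the 15-placebo-30 order is unaffected.
- *Late events are counted under the wrong condition.* Section 5.6.4 does not tabulate by visit, and nothing assigns an event to the visit where it is recorded.
- *Pre-existing symptoms cannot be separated from drug effects.* Onset times and the screening SMURF allow some separation; what is missing is a same-day comparator.
- *The whole SMURF looks back to the previous visit.* That recall period is attached to medications and health-care encounters; none is given for the specific queries.

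**Conclusion.** The inconsistency stands and should be resolved. If 4.3 and 5.2.1 govern, no imaging visit has a pre-dose symptom record. Events starting after the form at the 15 mg visit, about 1.75 to 2.75 h post-dose, are first systematically asked about after 30 mg in two of three orders, and events starting after the Visit 3 form have no later scheduled form. If Section 7 governs and means a SMURF before and after MEG at every visit, the first two gaps close and the third remains.

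The size is modest. A descriptive secondary endpoint is affected, not the MEG analyses, and spontaneous reports remain possible. The order count needs only the 3.2 table. The figure of about 27 subjects assumes equal allocation. The exposure shares are not estimates of how many events would be missed.

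**What to change.** - Reconcile 4.3, 5.2.1, Table 1 and Section 7 so that all state the same SMURF timing within each imaging visit, including what the pre- and post-MEG phrase covers at the first and last visits. Which timing applies, and any action taken on the answers, is for the investigators to state.
- In making that choice, note that the pre- and post-MEG reading of Section 7 would supply a same-day pre-dose record with the same form.
- In 5.6.4, summarise adverse events by the most recent condition received before onset, using the onset date and time from 7.2. Where a same-day pre-dose SMURF exists, count a same-day event as emergent only if it is new or worse than on that form.
- State whether events starting after the Visit 3 form are to be sought, and how.

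The cost is wording in five places. If two forms are chosen, add about 20 minutes per visit: Visit 2 goes from 250 to 270 min, or 280 min with a second 10-minute set of vital signs. At the first and last visits this may be physician time, since Section 7 has the physician give the form in person. The analysis rule needs no new data.
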